### 11.3 Sample Size Considerations

Sample size calculation for the pilot study has been provided in Section 11.2.

## 12 Source Documents and Access to Source Data/Documents

Study staff will maintain appropriate medical and research records for this study, in compliance with ICH E6, and regulatory and institutional requirements for the protection of confidentiality of subject information. Study staff will permit authorized representatives of SKCC and regulatory agencies to examine (and when required by applicable law, to copy) research records for the purposes of quality assurance reviews, audits, and evaluation of the study safety, progress and data validity. The only source documents outside of standard medical records available in the EMR will be the patient surveys and record of setup measurement shifts.

## **13 Quality Control and Quality Assurance**

The PI or a Co-I's will be present at the time of CBCT for patients undergoing MID placement for the first placement. Radiation therapists will be supervised by the PI or a Co-I for at least 2 MID placements, and shown proficiency in its use (correct application and patient setup) before they are not supervised.

Translational shifts will be verified by the PI or a Co-I and recorded in a secure electronic spreadsheet. Entries will be verified by radiation therapists. Surveys will be reviewed by clinic nurses to ensure all questions have been completed. Survey data will be recorded.

## **14 Ethics/Protection of Human Subjects**

### **14.1 Ethical Standard**

The investigator will ensure that this study is conducted in full conformity with the principles set forth in The Belmont Report: Ethical Principles and Guidelines for the Protection of Human Subjects of Research, as drafted by the US National Commission for the Protection of Human Subjects of Biomedical and Behavioral Research (April 18, 1979) and codified in 45 CFR Part 46 and/or the ICH E6.

### **14.2 Institutional Review Board**

The protocol, informed consent form(s), recruitment materials, and all subject materials will be submitted to the IRB for review and approval. Approval of both the protocol and the consent form must be obtained before any subject is enrolled. Any amendment to the protocol will require review and approval by the IRB before the changes are implemented in the study.

### **14.3 Informed Consent Process**

Informed consent is a process that is initiated prior to the individual agreeing to participate in the study and continues throughout study participation. Extensive discussion of risks and possible benefits of study participation will be provided to subjects and their families, if applicable. A consent form describing in detail the study procedures and risks will be given to the subject. Consent forms will be IRB-approved, and the subject is required to read and review the document or have the document read to him or her. The investigator or designee will explain the research study to the subject and answer any questions that may arise. The subject will sign the informed consent document prior to any study-related assessments or procedures. Subjects will be given the opportunity to discuss the study with their surrogates or think about it prior to agreeing to participate. They may withdraw consent at any time throughout the course of the study. A copy of the signed informed consent document will be given to subjects for their records. The rights and welfare of the subjects will be protected by emphasizing to them that the quality of their clinical care will not be adversely affected if they decline

to participate in this study. The consent process will be documented in the clinical or research record.

#### **14.4 Exclusion of Women, Minorities, and Children (Special Populations)**

Children are excluded from this study as they often require general anesthesia or sedation during radiation therapy to tolerate the standard thermoplastic mask. Both males and females patients with head and neck cancers or intracranial tumors who require RT will be eligible for the trial.

#### **14.5 Subject Confidentiality**

Subject confidentiality is strictly held in trust by the investigators, study staff, and the sponsor(s) and their agents.

The study protocol, documentation, data, and all other information generated will be held in strict confidence. No information concerning the study or the data will be released to any unauthorized third party without prior written approval of the sponsor.

The study monitor or other authorized representatives of the sponsor may inspect all study documents and records required to be maintained by the investigator, including but not limited to, medical records (office, clinic, or hospital) for the study subjects. The clinical study site will permit access to such records.

#### **14.6 Future Use of Stored Specimens and Other Identifiable Data**

Survey data will be held in a secure network drive until 3 years after the completion of the study.

### **15 Data Handling and Record Keeping**

The investigators are responsible for ensuring the accuracy, completeness, legibility, and timeliness of the data reported. All source documents should be completed in a neat, legible manner to ensure accurate interpretation of data. The investigators will maintain adequate case histories of study subjects, including accurate case report forms (CRFs), and source documentation.

Data will be entered into an electronic spreadsheet by a study team member and verified by a Radiation Therapist. Data will be stored on password protected computers on internal network drives. Survey responses will be inputted electronically by a study team member. Electronic copies of records will be kept for 3 years after completion of study.

#### **15.1 Data Management Responsibilities**

Data collection and accurate documentation are the responsibility of the study staff under the supervision of the investigator. All source documents and laboratory reports must be reviewed by the study team and data entry staff, who will ensure that they are accurate and complete. Unanticipated problems and adverse events must be reviewed by the investigator or designee.

---

## **15.2 Data Capture Methods**

As described in 15.1, data will be recorded electronically and stored on a password protected, secure network drive.

### **Types of Data**

Translational data and questionnaire data will be collected.

## **15.3 Study Records Retention**

Study records will be maintained for at least three years.

## **15.4 Protocol Deviations**

A protocol deviation is any noncompliance with the clinical study protocol, Good Clinical Practice, or Manual of Procedures requirements. The noncompliance may be on the part of the subject, the investigator, or study staff. As a result of deviations, corrective actions are to be developed by the study staff and implemented promptly.

All deviations from the protocol must be addressed in study subject source documents and promptly reported to the IRB and other regulatory bodies according to their requirements.

# **16 Study Finances**

## **16.1 Funding Source**

Study will be financed in cooperation with the Department of Radiation Oncology and Thomas Jefferson University Hospital Innovation Pillar.

## **16.2 Conflict of Interest**

Any investigator who has a conflict of interest with this study (patent ownership, royalties, or financial gain greater than the minimum allowable by their institution, etc.) must have the conflict reviewed by a properly constituted Conflict of Interest Committee with a Committee-sanctioned conflict management plan that has been reviewed and approved by the study sponsor prior to participation in this study. All Jefferson University Investigators will follow the TJU Conflicts of Interest Policy for Employees (107.03).

## **16.3 Subject Stipends or Payments**

Subjects will not receive any stipends or payments for participation in this study.

# **17 Publication and Data Sharing Policy**

The PI will have primary oversight and responsibility for the publication of these trial results. As this is a small feasibility study it is not required to be reported to the FDA. There is no NIH funding involved in this trial so it is not subject to NIH public access guidelines.

## Appendices

### APPENDIX A: SCHEDULE OF EVENTS

Procedures		Screening /Baseline (Day -28 to)	Study Visit 1 (Day 1)	Study Visit 3 (Day 8 ± 5)	Study Visit 4 (Day 15 ± 5)	Visit 5 Last day of treatment ± 5 Days
Signed Consent Form	X					
Assessment of Eligibility Criteria	X					
Review of Medical	X					
CT Simulation A		X				
Study Intervention (MID) B		X	X	X		
Questionnaire		X	X	X		
Physical Examination	Complete	X				
	Symptom- Directed		X	X	X	
Assessment of Adverse Events			X	X	X	

- A. CT Simulation will be with both thermoplastic mask and with MID
- B. Setup verification for MID application will be done with CBCT. No treatment to be given to patients with MID immobilization.

## APPENDIX B: PROMIS

PROMIS - Ca Item Bank v1.0 - Emotional Distress - Anxiety

### Emotional Distress-Anxiety

Please respond to each item by marking one box per row.

In the past 7 days...

		Never	Rarely	Sometimes	Often	Always
		1	2	3	4	5
EDANX27	I felt something awful would happen .....					
EDANX28	I felt uneasy .....					
EDANX29	I felt anxious.....					
EDANX30	I felt upset.....					
EDANX31	I had difficulty calming down .....					
EDANX32	I felt fearful.....					
EDANX33	I felt frightened.....					
EDANX34	I felt terrified.....					
EDANX35	I was concerned about my mental health .....					
EDANX36	I felt indecisive .....					
EDANX37	I had sudden feelings of panic .....					
EDANX38	I felt fidgety .....					
EDANX39	I felt like I needed help for my anxiety ....					

PROMIS - Ca Item Bank v1.0 - Emotional Distress - Anxiety

In the past 7 days...

	Never	Rarely	Sometimes	Often	Always	
	1	2	3	4	5	
EDANX00	I felt worried.....					
EDANX04	I felt nervous.....					
EDANX01	I had trouble relaxing.....					
EDANX06	I felt tense.....					
EDANX01	My worries overwhelmed me.....					
EDANX00	It scared me when I felt nervous.....					
EDANX06	Many situations made me worry.....					
EDANX05	I had unpleasant thoughts that wouldn't leave my mind.....					
EDANX09	I worried about dying.....	

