## Study Summary

Title:	A SINGLE INSTITUTION PILOT STUDY USING A HEAD AND NECK MASKLESS IMMOBILIZATION DEVICE (MID) FOR PATIENTS BEING TREATED FOR HEAD AND NECK CANCERS OR INTRACRANIAL TUMORS WHO REQUIRE RADIATION THERAPY
Précis:	Patients undergoing radiation therapy (RT) for head and neck cancers or intracranial tumors will undergo CT simulation and port films with the standard thermoplastic mask. On two separate treatment days they will be positioned with the MID after treatment is delivered with thermoplastic mask setup. Cone beam computed tomography (CBCTs) imaging obtained using the RT treating machine will be used to determine degree of setup variance. No RT will be delivered to patients while positioned with the MID.
Objectives:	
Primary: The primary objective of this study is to determine the setup accuracy and reproducibility of the MID in patients being treated for head and neck cancers or intracranial tumors who require radiation therapy.
 
Secondary: To assess the patient comfort and quality of life using the MID when compared to the standard thermoplastic mask.

Population:	24 male or female patients who are at least 18 years old, and are being treated for head and neck cancers or intracranial tumors which requires radiation therapy.
Phase:	Pilot
Number of Sites:	1 (Thomas Jefferson University)
Description of Intervention:	Maskless immobilization device (MID) that immobilizes the head and neck of a patient for RT with the use of two straps (one over the forehead and the other over the chin).
Study Duration:	50 months
Subject Participation Duration:	2-7 weeks
Estimated Time to Complete Enrollment:	48 months

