## 1.2 Rationale for the Proposed Study

The combination of the force gauge and strap for patient immobilization is the subject of intellectual property and does not exist outside this protocol. We propose that this combination allows for a safer application and reproducible immobilization of the patient compared to straps without force gauge quantification of pressure applied. However, the purpose of this study is not to evaluate safety, as the risk to patient with strap immobilization is extremely low. No radiation therapy will be delivered to the patient with MID immobilization.

The MID will be applied to the patient at CT simulation and two points during the treatment schedule, and no treatment will be delivered while the MID is applied to the patient. This will be two arbitrary time points to assess the degree of setup error compared to the gold standard of the thermoplastic mask. The patient population will be those patients being treated for head and neck cancers or intracranial tumors that requires radiation therapy (RT). This population is selected as the treatment fields are simple, and the setup position can be accurately verified by CBCT.

**SPECIFIC AIM 1:** To assess setup accuracy and reproducibility of the novel MID. We hypothesize that the degree of error with the novel MID will be similar to that of a thermoplastic mask.

---

---

**SPECIFIC AIM 2:** To assess the patient comfort and quality of life using the MID. We hypothesize that patients will have decreased claustrophobia symptoms and/or anxiety when immobilized with the MID compared to the thermoplastic mask.

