#### 2.2.3 Exploratory

## 3 Study Design

This is a single-institution, pilot study using a MID for RT treatment immobilization of patients being treated for head and neck cancers or intracranial tumors who require radiation therapy.. The patient population will be outpatient based, all of them receiving RT to treat head and neck cancers or intracranial tumors, assessed by CBCT and patient QOL surveys over the duration of their radiation treatment. There will only be a single study arm in which all patients receive RT with the thermoplastic mask but also receive CBCT imaging with the MID to assess the setup accuracy and reproducibility. Patient tolerance of the MID will be assessed through a survey delivered the day of MID use. Setup accuracy will be evaluated by comparing translational shifts required with MID to shifts required with thermoplastic mask. The last QOL evaluation will be at the completion of the patient's radiation treatment. **No radiation therapy will be delivered with MID immobilization.**

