# 6 Study Schedule

CT simulation	Port films	Fraction A	Fraction B
Day 1	Day 8	Day 8 ± 5	Day 15 ± 5
Thermoplastic mask immobilization	Thermoplastic mask immobilization + CBCT	Thermoplastic mask immobilization + CBCT	Thermoplastic mask immobilization + CBCT
		RT*	RT*
MID		MID + CBCT	MID + CBCT

\*RT is standard of care and will only be given while patients are immobilized with the standard thermoplastic mask.

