### **6.3 Treatment Period**

Visit 1, Day 1

CT simulation with thermoplastic mask. CT simulation with MID. Survey for anxiety and comfort. Symptom directed physical examination. Record any adverse events.

Visit 3, Day 8 ± 5

MID application and setup verification with CBCT. Survey for anxiety and comfort. Symptom directed physical examination. Record any adverse events.

Visit 4, Day 15 ± 5

MID application and setup verification with CBCT. Survey for anxiety and comfort. Symptom directed physical examination. Record any adverse events.

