### **6.4 End of Treatment Study Procedures**

#### **Final Study Visit (Final Visit, Last day of RT± 5)**

Final visit should occur on the last day of treatment. Patient is assessed for any adverse events. No further follow-up designated.

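### The Aim 2 questionnaire is never identified; the only form in the text, a general 7-day anxiety bank, could not compare MID with mask, and Section 11.2 states no within-patient term

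*Combined protocol and SAP*

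**What the plan says.** Section 1.2 states the Aim 2 hypothesis: "We hypothesize that patients will have decreased claustrophobia symptoms and/or anxiety when immobilized with the MID compared to the thermoplastic mask". Sections 2.2.2 and 11.1 make the outcome a questionnaire on pain, discomfort and anxiety, comparing time in the MID with time in the mask.

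The body describes the measure in several ways and never names an instrument:

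- Section 3 speaks of QOL surveys during treatment, and separately says: "Patient tolerance of the MID will be assessed through a survey delivered the day of MID use".
- Section 6.3 lists at both treatment-day visits: "MID application and setup verification with CBCT. Survey for anxiety and comfort". A survey is also listed at Visit 1. Which device is rated is not stated.
- Section 11.2 calls the data preference survey scores for mask versus MID, taken from the same patients and compared with a cumulative logistic regression model.

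The one form in the text is Appendix B, the PROMIS-Ca anxiety bank, with the stem "In the past 7 days". No section of the body refers to it.

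On exposure, the Study Summary says: "On two separate treatment days they will be positioned with the MID after treatment is delivered with thermoplastic mask setup". The Section 6 table adds: "RT is standard of care and will only be given while patients are immobilized with the standard thermoplastic mask". On Day 1, CT simulation is done with both devices (Section 6.3; Appendix A, note A).

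On the last assessment, Section 3 says: "The last QOL evaluation will be at the completion of the patient's radiation treatment". Section 6.4 lists for that visit only: "Patient is assessed for any adverse events. No further follow-up designated".

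**The concern.** Aim 2 is a contrast between two devices within each patient. It needs either a rating attached to each device or a direct preference. A reader who takes the appended form as the endpoint measure finds neither, and the data could not be recovered afterwards. A reader who assumes another survey cannot tell what is asked, or after which device.

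Preference scores and device-specific ratings are also different kinds of data with different analyses. Leaving the choice open leaves the model open too. Section 11.2 says who supplies the scores, but not how the correlation between scores from one patient is handled. The direction of the resulting error depends on which kind of data is collected.

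The setup-accuracy aim is not affected.

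**Working it through.** **1. Plan's own figure.** None exists for Aim 2: the documents give no score SD, correlation, effect size, margin or power. The 91% power in Section 11.2 concerns setup error. It reproduces at 90.7% (two-sample t-test, 12 per group, one-sided 5%, distance to margin 0.5 − (−1.0) = 1.5 mm, SD 1.2 mm) and does not bear on this point.

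**2. Content of the form.** Appendix B prints 13 + 9 = 22 items.

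| Needed (Sections 1.2, 2.2.2, 11.1, 11.2) | Printed items naming it |
|---|---|
| Mask or MID | 0 of 22 |
| Pain | 0 of 22 |
| Physical discomfort | 0 of 22 |
| Claustrophobia | 0 of 22 |
| Preference | 0 of 22 |
| General anxiety, not tied to a device | the bank as a whole |

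**3. Recall window.** All three MID sessions share a day with a mask session. At both treatment-day visits the MID follows treatment in the mask, so a 7-day answer that covers the MID also covers the mask. A copy completed after the MID would still include that day's mask session and those of the preceding week. At Day 1 the window is mostly days before either device was used. No treatment-day score therefore refers to the MID alone.

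**4. Analysis.** All correlations ρ = 0.3, 0.5, 0.7 are assumptions.

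*One rating per device per patient, treated as independent.* The variance of the difference is 2σ²/n if pairing is ignored and 2σ²(1−ρ)/n if it is used, so the SE ratio is 1/√(1−ρ):
- 1/√0.7 = 1.20
- 1/√0.5 = 1.41
- 1/√0.3 = 1.83

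This is exact for mean scores and a guide for a cumulative logit. A simulation closer to the named model used 24 patients, a five-level score and 4,000 runs. Its test was the tie-corrected rank-sum test, which is the score test of a cumulative logit with device as the only covariate. With no patient-by-device variation:

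| ρ | Type I error, unpaired | Power for a 0.4 latent-SD shift, unpaired | Same, paired t-test |
|---|---|---|---|
| 0.3 | 2.4% | 21.5% | 31.5% |
| 0.5 | 0.9% | 18.4% | 40.2% |
| 0.7 | 0.3% | 15.0% | 56.8% |

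*Preference scores from V visits, pooled as independent.* The design effect is DE = 1 + (V−1)ρ and type I error is 2(1 − Φ(1.96/√DE)):

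| ρ | V = 2: DE, type I | V = 3: DE, type I | V = 3, simulated |
|---|---|---|---|
| 0.3 | 1.3, 8.6% | 1.6, 12.1% | 11.2% |
| 0.5 | 1.5, 11.0% | 2.0, 16.6% | 15.3% |
| 0.7 | 1.7, 13.3% | 2.4, 20.6% | 19.0% |

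The last column is from 20,000 runs with 24 patients, a five-level scale and a t-test against neutral. The same test on per-patient means gave 5.0%, 5.0% and 4.9%.

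*Device-specific ratings from three visits, pooled as independent (rank-sum).* Type I error was 2.5%, 0.9% and 0.2% with no patient-by-device variation, and 12.9%, 12.2% and 10.6% with a latent patient-by-device variance of 1.0. The error can go either way.

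**The case against.** **A separate device survey is the more natural reading.** Section 3 mentions both QOL surveys and a survey on the day of MID use, and the descriptions in Sections 2.2.2, 6.3 and 11.2 do not fit the PROMIS form. On that reading PROMIS-Ca is a general measure and the defect is a missing name or attachment. The available text stops inside Appendix B, and the table of contents omits Appendix B altogether, so it cannot show that nothing followed. This stands. A reader might infer that no device-specific survey exists and that Aim 2 is bound to fail; the documents do not support that. They do show that no instrument is named and no timing is given for each device.

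**Section 11.2 never says that visits are pooled as independent.** This stands too. A reader might infer that the planned analysis has a type I error of up to 21%. That figure belongs to three pooled preference scores at the highest assumed correlation. One preference score per patient, an equally open reading, has no inflation. The preference simulation also tests against neutral with a t-test rather than fitting the named model, so it illustrates the effect of pooling and is not the plan's operating characteristic. What remains is that the stated model has no term for pairing or repeat visits.

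**This is a secondary aim of a 24-patient pilot.** True, and it limits the weight. Aim 2 is nevertheless a stated hypothesis with a named comparative model.

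**Conclusion.** The point holds in a conditional form and should be fixed.

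- *Unconditional:* the body does not identify the Aim 2 instrument or its timing for each device; Section 11.2 states no within-patient term for scores from the same patients; Sections 3 and 6.4 disagree on an end-of-treatment QOL evaluation.
- *Conditional on Appendix B being the endpoint measure:* it yields no separate MID and mask scores, and 0 of 22 items measure pain, physical discomfort, claustrophobia or preference, so it cannot measure the stated endpoint.
- *Size of the analysis problem, at assumed correlations of 0.3 to 0.7:* SE about 1.2 to 1.8 times too large with one rating per device; type I error about 9–13% (two visits) to 11–21% (three visits) if preference scores are pooled as independent; no such problem with one preference score per patient. No single direction of error should be claimed.

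How far a 7-day score would dilute a device difference cannot be quantified from the documents, and the conclusion does not need it. It rests on item content and same-day use of both devices.

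**What to change.** 1. **Instrument.** Name the endpoint survey, append it, and state when it is given for each device. If no device-specific survey exists, give a few short items on pain, discomfort and anxiety in this device just now, after each device at each MID visit, plus one preference item at the last MID visit. Keep PROMIS-Ca only as a general anxiety measure.
2. **Analysis.** In Section 11.2 specify a cumulative logit with a patient random effect or patient-clustered variance, and with device and visit terms. Alternatively, use a paired analysis of per-patient mean differences.
3. **Schedule.** Reconcile the end-of-treatment QOL evaluation in Section 3 with the final visit in Section 6.4.
4. **Limitation.** State that on treatment days the MID always follows the mask, so device and order are confounded and model terms cannot separate them.

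**Cost:** about a minute of patient time per short form (an estimate), an IRB amendment, and a few lines in Sections 6 and 11.2. No extra visit or imaging is needed. If a suitable survey already exists, the instrument part costs only appending it and stating its timing.
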